7.10.1.3 Analysis of Objectives

Full details will be described in the Statistical Analysis Plan (SAP).

7.10.1.4 Demographic and Other Baseline Characteristics

Full details will be described in the Statistical Analysis Plan (SAP).

7.10.1.5 Extent of Device Usage

Exposure to treatment/device will be presented by using summary statistics for number of days with study treatment by each device group.

7.10.1.6 Adverse Events/Adverse Device Effects

Device-related serious adverse events will be tabulated. The overall incidence of device-related serious adverse events will be summarized and presented as a proportion and respective 95% exact binomial confidence interval. Additionally, an overview of events, to include total numbers of events, and total number of subjects with events will be tabulated and presented for all AEs, serious AEs, and device-related AEs and device-related serious AEs, as well as deaths. Events will be presented overall and by study arm.

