7.2.1.5 Day of Study Completion

The last day of the study will be determined by discharge, transition to mechanical ventilation and/or if the patient is unable to continue. The following will be recorded:

- Study Measurements
 - Height/Wt, BMI
 - Temperature
 - Blood Pressure
 - O₂ Saturation
 - PaO₂/FiO₂ ratio
 - Shortness of Breath (Yes / No)
 - Cough (Yes / No)
- Labs
 - Pro-Calcitonin
 - C-reactive protein

Clinical Investigation Plan

- Ferritin
- D Dimer
- CBC with differential
- Comprehensive metabolic panel
- nVNS stimulations
 - Total number of gammaCore® treatments administered
 - Date and time of stimulations
- Daily Tx Log
 - Oxygen Required (Yes / No)
 - Oxygen level (%) based on device type (HFNC / NC / Bipap / Optiflow)
 - Ventilator Dependence (Yes / No)
 - Date and time of Ventilation
 - Patient discharge home (Yes / No)
 - Date and time (in 24 hour format) of Discharge
 - Survival (Yes / No) with Date and Time of Death
- Clinical Improvement Scale
 - Concomitant medication assessment
 - Adverse event assessment

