7.6 Risk and Benefits of the Investigational Device and Clinical Investigation

The gammaCore Sapphire is being trialled for the acute and prophylactic treatment of CoViD-19 induced respiratory distress. The anticipated benefits include:

- No mechanical respirator required
- Significant reduction of number of days in hospital

There are no significant risks identified with the participation in this study however study patients can rarely experience transient symptoms such as:

- Muscle twitching, discomfort, or pain during stimulations
- Tingling, pricking or a feeling of “pins and needles” on the skin where the device is applied (paraesthesia or dysaesthesia) lasting beyond the treatment period
- Skin irritation/inflammation
- Dizziness

Study subjects will be exposed to potential risks and complications associated with gammaCore. These are anticipated to resolve shortly after discontinuation of the stimulation procedure without medical intervention or clinical sequelae. Occurrence of several of these events can be mitigated by the user repositioning the device on the neck and/or decreasing the stimulation intensity. Training on the positioning of the device and controlling the stimulation intensity is conducted at the time the device is provided to the subjects. In addition, the device is provided with detailed Instruction for Use. These potential anticipated adverse events include, but are not limited to:

- Application site discomfort (4.85%)
- Application site irritation/redness (3.74%)
- Local pain, face/head/neck area (including toothache) (3.00%)
- Muscle twitching and/or contractions, face/head/neck area (including facial droop and/or lip pull) (3.47%)
- Headache/migraine (2.56%)
- Dizziness (2.00%)
- Tingling, pricking or a feeling of “pins and needles” on the skin where the device is applied (paresthesia/dysesthesia) (1.63%)

NOTE: When all available safety data was pooled from all studies, the following AEs occurred in >1% of patients, but less than < 5% (there were no reported side effects that occurred in >5% of study patients) All adverse events occurred in at least 1 in 100 (1%) patients and are therefore “common”.

Risks associated with blood draws

- Pain or discomfort from needle
- Bleeding
- Infection

Pregnancy:

It is unknown whether gammaCore can harm an unborn child if used during pregnancy. If you are pregnant, you will not be allowed to participate in this study.

The product will be used at the hospital.

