7.8.1 Adverse Event/Adverse Device Effect Definitions

Adverse Event

Any untoward or unfavorable medical occurrence in a human subject, including any abnormal sign (for example, abnormal physical exam or laboratory finding), symptom, or disease, temporally associated with the subject's participation in the research, whether or not considered related to the subject's participation in the research

Adverse Device Effect

Adverse event related to the use of an investigational medical device.

Note 1: This definition includes any event resulting from insufficiencies or inadequate instructions for use, deployment, implantation, installation, or operation, or any malfunction of the investigational medical device.

Note 2: This definition includes any event that is a resulting from a user error or from intentional misuse of the investigational medical device.

7.8.2 Serious Adverse Event/Serious Adverse Device Effect/Unanticipated Adverse Device Effect Definitions

Serious Adverse Event

An adverse event is considered serious and should be reported to IRB when the patient outcome is:

- **Death**
- **Life-threatening** - the patient was at substantial risk of dying at the time of the adverse event, or use or continued use of the device or other medical product might have resulted in the death of the patient.
- **Hospitalization (initial or prolonged)** - admission to the hospital or prolongation of hospitalization was a result of the adverse event. Emergency room visits that do not result in admission to the hospital should be evaluated for one of the other serious outcomes (e.g., life-threatening; required intervention to prevent permanent impairment or damage; other serious medically important event).
- **Disability or Permanent Damage** - if the adverse event resulted in a substantial disruption of a person's ability to conduct normal life functions, i.e., the adverse event resulted in a significant, persistent or permanent change, impairment, damage or disruption in the patient's body function/structure, physical activities and/or quality of life.
- **Congenital Anomaly/Birth Defect** - suspected exposure to a medical product prior to conception or during pregnancy may have resulted in an adverse outcome in the child.

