7.8.4 Reporting of Adverse Events/Adverse Device Effects

7.8.4.1 Methods for Eliciting Adverse Events/Adverse Device Effects

All patients will be carefully monitored for the occurrence of AEs during the investigation period from the run-in to the completion of follow up. The Clinical Investigator will collect AE information using non-leading questions such as "have you experienced any new health problems or worsening of existing conditions". Events directly observed or spontaneously volunteered by patients will also be recorded.

Clearly related signs, symptoms and abnormal diagnostic procedure results should be grouped together and reported as a single diagnosis or syndrome whenever possible.

All AEs including but not limited to events reported by the patient or reported in response to an open question by the Clinical Investigator or member of this team, which fall into any of the above definitions must be recorded as an AE in the CRF and should include the following information.

- Brief description of the event (diagnosis)
- Start date (and time, if relevant)
- Stop date (and time, if relevant) (or resolution)
- Severity
- Action taken regarding the medical device
- Opinion on causality
- Seriousness
- Outcome

Severity

Severity describes the intensity of an event and will be assessed as:

Mild

The AE does not interfere in a significant manner with the patient's normal functioning level. It may be an annoyance.

Moderate

The AE produces some impairment of function but not hazardous to health. It is uncomfortable and/or an embarrassment.

Severe

The AE produces significant impairment of functioning or incapacitation and/or it is a hazard to the patient.

If an AE changes in severity, it should be reported as an AE of new severity but with the same description.

Causality (Adverse Device Effects/ADE)

Causality will be assessed as:

- Related (definitely, possible or probable) - A causal relationship between the clinical investigational medical device and the AE is at least a reasonable possibility, i.e. there is evidence or argument suggesting a causal relationship.
- Not related - There is no indication that the AE was caused by the clinical investigational medical device.

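### Adverse events are counted by arm over a window that closes at discharge or ventilation, so the arm with the shorter window can show fewer events without lower risk

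*Combined protocol and SAP*

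**What the plan says.** Section 7.10.1.6 specifies the AE overview: "total numbers of events, and total number of subjects with events will be tabulated and presented for all AEs", with the same two measures for SAEs, device-related AEs, device-related SAEs and deaths. On layout it adds: "Events will be presented overall and by study arm". Only the overall incidence of device-related SAEs is to be "summarized and presented as a proportion and respective 95% exact binomial confidence interval".

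The observation window is set elsewhere. Section 7.2.1.5 says: "The last day of the study will be determined by discharge, transition to mechanical ventilation and/or if the patient is unable to continue". Footnote e to the flow chart in section 7.2.2 repeats this. Section 7.8.4.1 has AEs monitored "from the run-in to the completion of follow up", but no visit is scheduled after the study completion day.

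Treatment is expected to change the window. Section 7.6 lists among the anticipated benefits: "Significant reduction of number of days in hospital". Avoiding a mechanical respirator is the other benefit listed there.

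Section 7.10.1.5 describes exposure by "summary statistics for number of days with study treatment by each device group". These are days of device treatment and are not linked to the AE tables.

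**The concern.** A count of events, or of patients with an event, reflects both the daily risk and the number of days watched. Here the days watched are cut short by two opposite outcomes: recovery to discharge and deterioration to ventilation. If the arms differ in either, their counts cover different amounts of time, and the table in section 7.10.1.6 does not show that.

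This matters because showing the device to be safe is a stated aim (section 6). If the device shortens stay, part of any apparent safety advantage could come from shorter observation. If one arm reaches ventilation sooner, its window also shortens, and a lower AE count there would not be reassuring. The exposed rows are all AEs and all SAEs.

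**Working it through.** **Inputs.** The documents give no AE rate, length of stay or ventilation rate, so there is no planned figure to reproduce. The only design number used is 30 patients per arm (section 7.4.1: up to 60, allocated 1:1). All rates and windows below are assumptions.

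**Step 1: equal daily risk, unequal windows.** With daily rate λ and mean window d, expected events in 30 patients are 30 × λ × d. If every patient stays exactly d days, the share with at least one AE is 1 − exp(−λd).

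| λ per day | Mean window (days) | Events per 30 | Patients with an AE |
|---|---|---|---|
| 0.05 | 8 v 6 | 12 v 9 | 33% v 26% |
| 0.05 | 8 v 4 | 12 v 6 | 33% v 18% |
| 0.02 | 8 v 6 | 4.8 v 3.6 | 14.8% v 11.3% |

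In the first row, 30 × 0.05 × 8 = 12 and 30 × 0.05 × 6 = 9, which is 25% fewer events. Event counts need only the mean window. The percentages depend on how stays are distributed. With exponential stays the share is λ/(λ + 1/d), and 33% v 26% becomes 28.6% v 23.1%, in the same direction.

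Per 100 patient-days, the first row gives 12/(30 × 8) = 5 and 9/(30 × 6) = 5, so the difference disappears.

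**Step 2: one arm is ventilated sooner.** Assume a daily discharge hazard of 0.12 in both arms, a daily ventilation hazard of 0.06 v 0.02, and follow-up to at most 28 days. With total exit hazard h, the mean window is (1 − exp(−28h))/h:
- worse arm, h = 0.18: 5.52 days
- other arm, h = 0.14: 7.00 days

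Expected AEs per 30 patients, worse arm v other arm, at equal daily AE rates:
- 0.05 per day: 8.3 v 10.5
- 0.10 per day: 16.6 v 21.0
- 0.20 per day: 33.1 v 42.0

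The arm that deteriorates faster shows fewer events.

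**Step 3: when the direction reverses.**
- *Higher daily rate.* The break-even rate ratio equals the window ratio, 7.00/5.52 = 1.27. At a base rate of 0.10, a worse-arm rate 1.2 times higher still gives fewer events (19.9 v 21.0), while 1.5 times gives more (24.8 v 21.0).
- *Ventilation recorded as an AE.* This adds 30 × 0.06 × 5.52 = 9.9 events v 30 × 0.02 × 7.00 = 4.2. Totals become 18.2 v 14.7, 26.5 v 25.2 and about 43 v 46 for the three base rates, so the direction reverses in two of the three. Section 7.8.1 defines an AE as "Any untoward or unfavorable medical occurrence in a human subject" and goes on in equally broad terms. It does not say whether progression to ventilation is included.

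**The case against.** **The direction is not fixed.** Someone might infer that the arm that worsens sooner will necessarily look safer. Step 3 shows that it need not, and the AE definition leaves open the recording rule that helps decide the sign. This objection stands.

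**The information is available elsewhere.** Proportion ventilated, days to ventilation, live discharge, length of stay and mortality are all listed for comparison (sections 6 and 7.7.2). It would therefore be too strong to say that a shortened window could not be told from a true difference in risk: a reader could see that the windows differ, and why. That reader still could not form the rate. Length of stay, if it means the whole hospital stay, is not the AE window of a ventilated patient, and the device-days in section 7.10.1.5 give no denominator for controls, who receive no device.

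**The primary safety measure is barely touched.** It is treatment-related SAEs (section 7.7.3). With no device in the control arm, this is hardly a between-arm contrast. This stands and limits the point to all AEs and all SAEs.

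**There is some later follow-up.** AEs ongoing at withdrawal are followed (7.8.4.2), deaths within 30 days of treatment go to the IRB (7.8.5), and patients who discontinue for safety or lack of effectiveness are followed if possible (7.12). None of these collects new AEs in both arms to a common day, though the death row is less exposed than the others.

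**The study is small and descriptive.** Comparisons are nominal (7.10.1.2). For 12 v 9 events the Poisson standard deviation of the difference is √(12 + 9) = 4.6, which exceeds the artefact of 3. An 8 v 4 day contrast caused by ventilation alone would, under constant hazards, need about 50% v 0% ventilated, which would be obvious. That limits the likely size. It does not remove a systematic distortion from a table the safety board and later readers will use.

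**A separate SAP is promised.** Section 7.10.1 says so, and that SAP is not in the document reviewed, so it cannot be said that no adjustment is planned. But 7.10.1.6 lists its own outputs, whereas 7.10.1.3 and 7.10.1.4 leave their full details to the SAP.

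**Conclusion.** The point holds in a limited form. As written, section 7.10.1.6 presents AEs and SAEs by arm as counts over a window that ends with the patient's outcome, with no time at risk. With similar daily rates, the shorter-window arm can show fewer events without lower risk. In the illustration this is 25% fewer for 6 v 8 days, and a true daily rate ratio of up to 8/6 = 1.33 would be masked.

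These sizes rest on assumed rates and windows and on a constant daily hazard. The documents do not support reading this as a demonstrated bias in favour of the device, as a fixed direction of error, or as a defect in the primary safety measure. It is a correctable weakness in a descriptive safety table.

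**What to change.** In section 7.10.1.6, or in the separate SAP, add beside the existing counts:

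- Patient-days at risk by arm, from randomisation to study exit, for the same patients and grouping as the counts.
- AEs and SAEs per 100 patient-days by arm with 95% confidence intervals that allow for several events in one patient.
- Time to first AE by arm as a check, because a single rate assumes a roughly constant hazard. If AEs cluster early, a shorter window raises the rate.
- Reason for exit (discharge, ventilation, death, other) by arm in the same table.
- A statement of whether transition to ventilation is counted as an AE, applied identically in both arms.
- For device-related AEs, a denominator of device-treatment days in the active arm only.

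The cost is wording, a few derived variables and slightly more analysis work. Randomisation is on Day 0, and the dates and times of ventilation, discharge and death are already recorded, so no new data are needed. One limit remains: events after exit stay unobserved, and only collection to a common fixed day in both arms would change that.

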7.10.2 Handling of Drop-outs and Missing Data

Outliers will be included in summary tables and listings, and will not be handled separately. Available data from prematurely withdrawn patients will be included in the analysis as far as possible. If data are only partially completed, the available data will be reported as an per protocol evaluation

7.10.3 Determination of Sample Size

This is one of the first studies of GammaCore Vagus Nerve Stimulation treatment in COVID-19. There is no published data on anticipated effect size in humans. Hence, a formal power analysis could not be done.

Data will be presented using summary statistics. For example, categorical data may be presented as proportions and counts; continuous data may be presented with the mean, median, minimum, maximum, and/or standard deviations. Kaplan-Meier methodology may be used to present time to event data. All comparisons between active and control groups are nominal in nature; confidence intervals and p-values may be presented, but are not intended for inferential purposes.

7.10.4 Interim Analysis

An analysis of safety and feasibility was conducted on the first 20 patients who completed the hospitalization period. Only minor protocol deviations were noted with one SAE unrelated to device use. Neither incidence was a reportable event to the IRB.

7.10.5 Procedures for Reporting any Deviations from the Original Statistical Analysis Plan

Any deviation(s) from the original statistical analysis plan will be described and justified in a CIP Amendment and/or in a revised statistical analysis plan and/or in the final report, as appropriate.

7.11 Amendments to the Clinical Investigation Plan

Any change to the approved CIP must be documented in a written and numbered CIP amendment with a justification for the amendment. Changes to the CIP will only be implemented after written agreement has been obtained between the Principal/Coordinating Clinical Investigator and the IRB. electroCore will also be notified of any amendments or changes to the IRB approved CIP.

An amendment to the CIP may require notification or approval from IRB/IEC and, in many countries, the Competent Authority before implementation. Local requirements shall be followed.

7.12 Deviations from the Clinical Investigation Plan

Every effort should be made to comply with the requirements of the protocol. If the changes or deviations may affect the rights, safety, or welfare of participants, IRB/IEC approval is required. Deviations will be recorded with an explanation for the change. Corrective action will be implemented to avoid repeat deviations.

The reasons for any patient's withdrawal and discontinuation from the investigation will be recorded. If such discontinuation is because of problems of safety or lack of effectiveness, the patient will still be followed up in the investigation, if possible.

7.13 Report and Publication

The CIP shall specify whether the results of the investigation will be submitted for publication or the extent to which and conditions under which the results of the clinical investigation will be offered for publication.

At the completion of the study, the Clinical Investigator may collaborate with the device manufacturer, electroCore, to review and use the data collected for publication purposes. If/when the Clinical Investigator chooses to publish results of the study, the PI will provide electroCore with the final clinical study report summarizing the study and the results prior to publication.

All publications and presentations must be based upon the clinical investigation report.

8 ETHICS

8.1 Institutional Ethics Review

The final CIP, including the final version of the Patient Information and Consent Form, must be approved in writing by an IRB/IEC before enrollment of any patient into the investigation. The Clinical Investigator is responsible for informing the IRB/IEC of any amendment to the CIP, as per local requirements.

8.2 Ethical Conduct of the Clinical Investigation

The investigation will be conducted in compliance with applicable regulatory requirements and with the ethical principles of the latest revision of the Declaration of Helsinki as adopted by the World Medical Association (Appendix A).

8.3 Patient Information and Consent

All patients will receive written and verbal information regarding the investigation prior to any investigation-related procedures. This information will emphasise that participation in the investigation is voluntary and that the patient may withdraw from the investigation at any time and for any reason. All patients will be given the opportunity to ask questions about the investigation and will be given sufficient time to decide whether to participate in the investigation.

Before any investigation-related procedures, the informed consent will be signed and dated by the patient, a witness to signature, and by the Clinical Investigator who gave the patient the verbal and written information.

The consent specifies that data will be recorded, collected, processed and used in accordance with patient consent and applicable law.

9 PATIENT PROTECTION PROCEDURES

9.1 Procedures in Case of Medical Emergency

The Clinical Investigator is responsible for ensuring that procedures and expertise are available to cope with medical emergencies during the investigation.

9.2 Patient Data Protection

Minimal necessary data will be collected and stored on a hospital password protected research drive only accessible to the research staff. Risk of breach of confidentiality of this data has been minimized as much as possible. We have used the “minimum necessary” standard in choosing specific and pertinent data parameters for this research.

All key research team members having access to clinical data (containing PHI) being collected and analysed currently work within our system. Data containing PHI will be stored on secure, password-protected computers by the team and when necessary, will be securely emailed to other team members using only AHN.org email accounts (as per AHN IT Security Policy). Team members will use secure computers and systems to access and work with study spreadsheet data/files. When any information is shared with the sponsor, this will be de-identified. PHI will not be shared with the sponsor.

At the conclusion of data analysis for the protocol, identifiers will be stripped from the compiled datasheet to anonymize the dataset by the PI, or other team member with the goal that the data will be presented formally. Patient identifiers will be deleted and the dataset anonymized as soon as possible. We will comply with the AHNRI IRB “Records Retention” SOP #72 Section 4.6.1 which states “...for research involving PHI performed at AHN, the records will be retained for 10 years after the study is completed.”

